**Table 4      Confidence Interval for Selected Sample Sizes by Response Proportion**

Proportion	Margin	Lower CI	Upper CI	Sample Size
95.0%				
90.0%				
85.0%				
80.0%				

## 10.3 Data Management & Statistical Analysis

### 10.3.1 Data Analysis

A descriptive analysis will be conducted to assess the ease of use and confidence of use of the lebrikizumab pen. All participants having given an informed consent will be included in the analysis population.

The main endpoint of the study will be assessed via the mSQAAQ. The primary outcome reported from each individual question will be the proportion of participants responding “agreed” or “strongly agreed” to the question. Participants who do not complete an individual item in the mSQAAQ will have their remaining questions analyzed per instrument instructions.

Collected demographic information and health literacy level of study participants will be presented for the total analysis population as well as any selected sub-populations. A descriptive analysis of any AEs and/or product complaints reported during the study will be included for the total analysis population.

### **10.3.2 Data Quality Assurance**

Concentrics will act as the contract research organization (CRO) for the study and will conduct the study in a manner consistent with the general principles of Good Clinical Practices (GCP). Study site supervisory staff will be trained regarding all study procedures, including, quality control, CRFs, mSQAAQ, [9.10](#) documentation and communication with the CRO.

Quality checks will be performed by the data management team at Concentrics Research on all data collected to ensure completeness, accuracy and consistency of the data captured (e.g. all required fields are completed, follow-up questions were asked where appropriate). Any discrepancies or questions with respect to the data will be handled via queries sent to the research site for clarification and/or resolution.

### **10.4 Interim Analysis**

There is no plan to perform interim analyses for this study.

### **10.5 Handling of Missing Data**

Any participants who attend a study visit but do not complete the simulated injection and mSQAAQ [9.10](#) will be excluded from the analysis. Partial completion of the mSQAAQ will be analyzed per the instrument instructions.

## 11 Monitoring

Risk-based monitoring will be conducted for this study. The pre-study visit has been waived by the CRO.

The Site Initiation Visit will be combined with a virtual Investigator's Meeting. During this meeting the study protocol, objectives, methods, data collection and data entry procedures and adverse event procedures will be reviewed.

During the course of the study there will be 3 interim monitoring visits. Some visits will be on-site, and some will be remote. The CRA will review the eCRFs and source documents and review Study Device accountability.

One close-out visit is planned. At this visit, a final review of all documentation and data entry will be completed. Study Device accountability will be reviewed and the plan for Study Device return or destruction will be discussed.

## 12 Safety

### 12.1 Adverse Event Definition

An AE is defined as any untoward medical occurrence in a participant or clinical investigation (vital signs, physical change, etc.) that does not necessarily have a causal relationship with the treatment. An AE can be any unfavorable or unintended sign (including an abnormal finding on vital signs, physical change, etc.), symptom, or disease temporally associated with the use of an IP, whether or not related to the IP.

This includes any adverse occurrence that is new in onset or aggravated in severity, duration, or frequency from the baseline condition (including the physical examination), or abnormal results of diagnostic procedures (including vital sign abnormalities).

Examples of untoward medical events that should be considered AEs are those that:

- resulted in discontinuation from the study,
- required treatment or any other therapeutic intervention,
- required further diagnostic evaluation (excluding a repetition of the same procedure to confirm the abnormality),
- are associated with clinical signs or symptoms judged by the Investigator to have a significant clinical impact.

Examples of what an AE is not:

- A surgical procedure
- A situation where an untoward event did not occur, (e.g. a social hospitalization)
- The disease being studied, unless progression is more severe than anticipated
- Baseline conditions that have not worsened in severity or frequency
- Abnormal findings or test results (unless considered clinically significant in the opinion of the investigator or specifically defined elsewhere in the protocol) related to the disease being studied (unless more severe than expected).

### 12.2 Adverse Device Effect Definition

An adverse device effect (ADE) is any adverse event related to the use of an investigational medical device (This definition includes adverse events resulting from insufficient or inadequate instructions for use, deployment, implantation, installation, or operation, or any malfunction of the investigational medical device. Includes any event resulting from use error or from intentional misuse of the investigational medical device. Also includes 'comparator' if the comparator is a medical device.).

### **12.3 Procedures**

Adverse events will be gathered from the point that the informed consent is signed until participant leaves site on date of visit. Participants with unrelated adverse events will be followed for 7-days post AE. All SAEs, and related AEs will be followed until the event has resolved. This is a 1-visit study.

A description of the event or diagnosis including dates, severity, relationship to the device and/or IP, action taken and outcome, and whether or not the event was also serious, must be reported on the AE Case Report Form (CRF) for each adverse event.

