**Methodology:**

Following recruitment and pre-screening, qualified participants will be scheduled for an on-site visit at the research site. This is a one-visit study.

Once at the site, the site staff will:

1. Confirm the participant's identity by checking a government-issued ID such as a Driver's License.
2. Provide the Informed Consent document for the participant to review and sign.
3. Assign a participant ID number.
4. Reconfirm inclusion/exclusion criteria and demographics.
5. Administer urine pregnancy test for participants assigned female at birth (AFAB) unless considered individual not of childbearing potential (INOCBP)
6. Obtain medical history including approximate date of the participant's AD diagnosis, any previous or current AD treatments.
7. Administer the REALM Test.

8. Provide a study overview.
9. Provide training to the participant on the use of the device.
10. Site staff will observe participant injection experience using the injection pad.
11. Administer the modified Subcutaneous Administration Assessment Questionnaire (mSQAAQ)
12. End participant's study visit.

Adverse events (AEs) and product complaints will be gathered from the point that the informed consent is signed until participant leaves site on date of visit. Participants with adverse events will be followed for 7-days post AE, via phone call.

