## 5.7 Methods to Minimize Risks

Training on the study device will be provided by study staff prior to the participant performing the simulated injection. Training for correct sharps handling/disposal is part of the study training, and no cross contamination is expected due to each participant receiving their own device, as well as injecting drug into an injection pad. Participants will be instructed to place the base cap in the sharps container once it is removed from the device, so they do not have the temptation to recap. Study staff will monitor the participants at all times in the room and intervene should a dangerous situation occur.

Participants will be under direct supervision of the study staff when handling the device.

The following controls will be in place to prevent an accidental dose of drug product:

1. The participants will only handle the devices under direct supervision of study staff after receiving training.
2. Participants will be told that they should not inject themselves, and these devices will only be used for simulated injections into an injection pad.
3. If a participant appears to begin injecting themselves rather than the injection pad, the site staff will immediately interrupt the process and stop the participant from completing this self-injection.
4. In the unlikely circumstance that a participant does have an accidental needle stick or accidental injection, it is not likely the participant would receive a full dose since a full dose takes up to 15 seconds for delivery.

If a needlestick injury occurs or if a patient is exposed to drug, medical personnel will be available to address any potential medical issues or concerns. Clinical staff members will follow (monitor) the participant as per clinical judgment for a potential adverse event (AE) and follow the appropriate device-reporting procedures for 7 days following the visit.

More detailed information about the known and expected benefits and risks of lebrikizumab may be found in the lebrikizumab investigator's brochure (IB).

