### 12.8.1 Serious Adverse Event Reporting

Any SAE which occurs after the Informed Consent document is signed until participant leaves site on date of visit must be reported to Lilly. Lilly must be notified within 24 hours after the site/investigator becomes aware of the SAE.

If the Principal Investigator determines that the event is serious, the following procedures will be implemented:

- The Investigator will report the SAE directly to Lilly. Contacts for SAE reporting can be found in site training materials.
- Investigator will provide, at a minimum, the protocol number, participant's initials, participant number, date of the SAE, SAE term and relationship to IP and/or device. The SAE report form should be submitted with any supporting data available or copies of CRF pages.
- Advarra IRB will be notified of the SAE by the site within the timeframes described below:

1. Unanticipated problems that are serious adverse events should be reported to the IRB within 10 business days of the investigator becoming aware of the event.
2. Any other unanticipated problem should be reported to the IRB within 10 business days of the investigator becoming aware of the problem.

An initial report followed promptly by a complete report will be forwarded to Advarra IRB.

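### Section 5.7 monitors drug-exposed participants for 7 days, but AE gathering and SAE reporting stop when they leave the site; separately, 5.7 and the IFU disagree on base-cap disposal

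*Protocol*

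**What the plan says.** **Monitoring after exposure.** Protocol 5.7 begins: "If a needlestick injury occurs or if a patient is exposed to drug, medical personnel will be available". Staff are then to monitor that participant, using clinical judgment, for an AE that may yet occur, and to "follow the appropriate device-reporting procedures for 7 days following the visit". The trigger is the needlestick or exposure itself. No AE need have happened.

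**Collection and reporting.** Protocol 12.3 states: "Adverse events will be gathered from the point that the informed consent is signed until participant leaves site on date of visit". Section 9.2.5 and the synopsis give the same window for AEs. For serious events, 12.8.1 states: "Any SAE which occurs after the Informed Consent document is signed until participant leaves site on date of visit must be reported to Lilly". The synopsis also closes product complaints at that point ("product complaints will be gathered from the point that the informed consent is signed until participant leaves site on date of visit"), whereas 12.9.2 and 12.9.3 give no cutoff for them.

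**Follow-up.** The synopsis provides: "Participants with adverse events will be followed for 7-days post AE, via phone call". Section 9.2.5 limits follow-up to participants whose AE arose during the visit. Sections 12.3 and 12.7 follow unrelated AEs for 7 days, and related AEs and all SAEs to resolution.

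**Base cap.** Section 5.7 has participants drop the removed cap into the sharps container, so that they are not tempted to recap. Step 1 of the IFU (Appendix 14.1) tells them to discard it in the trash and not to put it back on.

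**The concern.** The pens hold active drug, and the protocol treats exposure as foreseeable. Section 5.6 lists a skin reaction from drug on the skin, and an injection site reaction or hypersensitivity after accidental injection. Section 6.3 justifies pregnancy testing by the risk of accidental exposure. Section 5.7 responds with a 7-day watch, but the sections that define what is collected and reported do not carry that watch forward. Staff could notice a listed reaction on day 2 while doing what 5.7 asks, and find that the written windows do not require it to be recorded as an AE or, if serious, reported to the sponsor.

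The cap instruction is a separate matter. Under 8.2 the IFU is reviewed in training and may be consulted during the injection, so the document in the participant's hands contradicts a control that 5.7 relies on.

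**Working it through.** There is no plan figure to reproduce. The check is a comparison of text.

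**Step 1: set the windows side by side.**

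| Protocol section | Who | Closes |
|---|---|---|
| 5.7, monitoring and device reporting | Needlestick or drug exposure, AE or not | 7 days after the visit |
| Synopsis, 9.2.5, 12.3, AE gathering | All participants | Departure from the site |
| 12.8.1, SAE reporting to the sponsor | All participants | Departure from the site |
| Synopsis, product complaints | All participants | Departure from the site |
| 12.9.2, 12.9.3, product complaints | All participants | No cutoff given |

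For a new event in an exposed participant, the difference is 7 − 0 = 7 days in which monitoring is planned but the written AE and SAE windows are shut.

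**Step 2: see whether a follow-up clause reopens the window.** The clauses in the synopsis, 9.2.5, 12.3 and 12.7 each start from an AE or SAE that already exists. Section 12.8.2 likewise deals with following known SAEs, including those still ongoing when the visit ends. None covers a participant who leaves without an event and develops one later.

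**Step 3: take out what is already covered.** A needlestick opens an AE form under 9.2.5. Under 12.5 a possible temporal or causal link is enough to call an AE related, and 12.7 follows related AEs to resolution. A participant with a needlestick is therefore already in follow-up. A distinct new reaction after departure is still outside the literal window, but it is likely to be seen.

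**Step 4: state what remains.** Four things must coincide: drug exposure without a needlestick (drug on skin is the obvious case), no AE before departure, a reaction that starts afterwards, and staff who apply 12.3 or 12.8.1 literally despite 5.7.

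**Step 5: size.** The expected number of uncollected events would be n × p × q × r, where
- n is the number enrolled, about 56 (protocol 6.1);
- p is the rate of exposure without a needlestick;
- q is the share of those with no AE at departure and a later reaction;
- r is the share of those reactions that go unrecorded.

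The documents give n only. Any probability would just reflect the values chosen for p, q and r, so none is quoted. Injection into a pad, prior training and direct supervision all suggest the number is very small.

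**Step 6: the cap.** One object at one step has two destinations: sharps container in 5.7, trash in the IFU. A sharps container is already among the supplies the IFU lists. The conflict is in wording that applies to every participant; that describes its reach, not its harm.

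**The case against.** The strongest reply is that 5.7 is the specific rule for exposed participants and 12.3 the general rule for everyone, so 5.7 governs. Watching for an AE makes little sense if one that is found is not recorded. Other text supports this:
- Table 2 marks AE and product-complaint management in an if-needed column after Visit 1. The same row label covers Visit 1, where collection plainly takes place.
- Section 12.9.3 requires recording when an event occurs, with no departure limit.
- The provisions on serious unexpected reactions (12.9) and unanticipated device effects (12.9.1) have no departure limit.
- Nor does the IRB rule in 12.8.1: "Any other unanticipated problem should be reported to the IRB within 10 business days of the investigator becoming aware of the problem".

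Much of this stands, and it narrows the gap. It does not close it. No collection section refers to 5.7, and the 7 days there can even be read as attaching to device reporting alone. Table 2 gives no onset window. Section 12.9.3 says how to record, not until when. The sponsor's clocks in 12.9 and its 10-working-day limit in 12.9.1 run from the sponsor's receipt of the information or notice, which is what 12.8.1 is meant to supply. The IRB and device-effect rules concern unanticipated problems, while the reactions at issue are foreseen in 5.6.

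On the cap, it is fair to say that either container disposes of it, that the IFU forbids recapping and that staff are in the room. That limits the harm but leaves the contradiction.

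A reader might go further and infer that exposed participants are left unwatched, or that reactions to needlesticks go unrecorded. The documents do not support either: 5.7 provides the watch, and 9.2.5, 12.5 and 12.7 largely cover needlesticks.

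**Conclusion.** Both parts hold as minor safety corrections to text that is wrong as written. For exposed participants the protocol plans 7 days of monitoring, while its AE and sponsor SAE windows allow none after departure and state no exception. The practical gap is drug exposure without a needlestick, no AE at departure and a later reaction. This rests on reading the cutoffs in 12.3 and 12.8.1 literally; a site that treats 5.7 as an exception would lose nothing.

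The number of events at stake cannot be derived from the documents and is probably very small. A reader might infer a measurable chance of lost safety reports, or a real rise in needlestick risk from the cap wording. With no exposure rate given, and with supervision and a recapping ban in place, neither can be claimed. The mSQAAQ response proportions and their confidence intervals are unaffected.

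**What to change.** **Windows.** In the synopsis, 9.2.5, 12.3 and 12.8.1, add one sentence to this effect: *For any participant with a needlestick or drug exposure at the visit, new-onset AEs, SAEs and product complaints through 7 days after the visit are collected and reported under section 5.7, with a follow-up phone call at the end of that period.* Keep the present window for everyone else.

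**Cap.** Change IFU step 1 so that the cap goes into the sharps container, and check that the training video agrees. Rewording 5.7 to say trash would also remove the conflict and would be cheaper, but it gives up the control that 5.7 describes, so changing the IFU is preferable.

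**Cost.** One sentence in four places, one IFU line, a check of the video, and IRB approval of the amendment (13.2). The running cost is one call per exposed participant. That is slightly firmer than the clinical judgment 5.7 allows, but a phone call is already the synopsis's follow-up method for participants with AEs. Design, sample size and analysis do not change.

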### **12.4 Severity**

Adverse events are graded according to seriousness and severity. The seriousness of an event is determined by the regulatory criteria in Section 13.7.

The Investigator will evaluate the severity of each AE. Adverse event severity will be graded as follows:

Mild: Awareness of symptoms but easily tolerated

Moderate: Discomfort enough to interfere with but not prevent daily activity

Severe: Unable to perform usual activity

### **12.5 Relationship**

The Investigator will judge the likelihood that the AE was related to the device or IP according to the following criteria:

- Not related: There is no possible temporal and/or causal relationship to the device or IP
- Related: There is a possible temporal and/or causal relationship to the device or IP

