15. SAFETY OUTCOMES

All outputs for safety outcomes will be based on the ENR. AE/SAE/Product complaints will be coded using the latest version of MedDRA at the time of data analysis. The MedDRA version used for a given output will be added in the footnote.

A listing by patient including each verbatim term, preferred term, start and end date, ongoing status (Yes/No), action taken, outcome, severity, seriousness, relationship to the device, and relationship to drug will also be provided.

A listing of adverse events, medications and product complaints will be provided. It will include patient responses to whether the participant experienced any adverse events during this study, whether the participant is currently taking any medication or therapy, whether the participant identified any product complaints, and whether a product complaint form was submitted to the study sponsor.

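### Protocol 12.5 lets timing alone make an adverse event 'Related', so in this one-visit study the label does little to separate coincidental events from those caused by the pen or the drug

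*Protocol*

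**What the plan says.** Protocol 12.5 introduces the assessment with "The Investigator will judge the likelihood that the AE was related to the device or IP according to the following criteria" and offers two categories. The positive one is "Related: There is a possible temporal and/or causal relationship to the device or IP". Its counterpart, built on the same phrase with a negation, is "Not related: There is no possible temporal and/or causal relationship to the device or IP".

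No other section says whether timing by itself is enough, or adds a causal requirement to either category.

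Protocol 12.1 defines an AE to include an event "temporally associated with the use of an IP, whether or not related to the IP". Protocol 12.3 sets the collection window: "Adverse events will be gathered from the point that the informed consent is signed until participant leaves site on date of visit".

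The label is then used in several places. In 12.3 the rule for events judged unrelated is "Participants with unrelated adverse events will be followed for 7-days post AE". For the remaining events the same section has a different rule: "All SAEs, and related AEs will be followed until the event has resolved". Protocol 12.7 makes the same split. Protocol 12.2 defines an adverse device effect (ADE) as an AE that is related to use of the device. SAP section 15 plans a by-patient listing in which "relationship to the device, and relationship to drug will also be provided".

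**The concern.** A relationship assessment should sort events by whether the product plausibly caused them. If closeness in time is sufficient, the assessment cannot do this in a study where everything after pen use happens within the same site visit. Take a headache that starts while the participant fills in the mSQAAQ and has no plausible link to the pen. It still meets *Related*.

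Three things depend on the label: how long a non-serious AE is followed under 12.3 and 12.7, whether an event is likely to be regarded as an ADE under 12.2, and how far the relationship columns of the SAP listing can be interpreted. The wording also sits badly with 12.1, where an event can be temporally associated with use and still be unrelated. Under the plain reading of 12.5, such an event could not be labelled unrelated.

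**Working it through.** The plan gives no figure to reproduce. The check is a logical one on the wording.

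**Inputs.** Let T mean that a temporal relationship is possible, and C that a causal relationship is possible. *Related* (12.5) can be read as 'T or C' or as 'T and C'. *Not related* (12.5) can be read as 'neither T nor C' or as 'not both T and C'.

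**Which events meet each reading**

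| Event | Related: T or C | Related: T and C | Not related: neither | Not related: not both |
|---|---|---|---|---|
| T and C | yes | yes | no | no |
| T only | yes | no | no | yes |
| C only | yes | no | no | yes |
| neither | no | no | yes | yes |

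**What each pair of readings does to a timing-only event (T only)**

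1. 'T or C' with 'neither': the categories are exact complements, and the event is *Related* on timing alone. This is the plain reading.
2. 'T or C' with 'not both': the event meets both categories, so they overlap.
3. 'T and C' with 'neither': the event meets no category, so there is a gap.
4. 'T and C' with 'not both': exact complements again, but the event is now *Not related*.

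A timing-only event can therefore be *Related*, both, neither or *Not related*. The text does not say which reading applies.

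**How often T holds.** Under 12.3, collection runs from consent to departure on the day of the visit. An AE that starts after the pen is handled is always close in time to that handling, so T holds for nearly all such events. An AE between consent and pen handling has no temporal link to use and is not caught. On reading 1, the label thus mainly records whether the event began before or after the pen was handled, not whether the pen or the drug caused it.

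**Where the label acts**

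| Use | Does it depend on the 12.5 label? |
|---|---|
| Follow-up of non-serious AEs (12.3, 12.7) | Yes |
| Follow-up of serious AEs (12.3, 12.7, 12.8.2) | No; until resolved in every case |
| ADE definition (12.2) | In part; it needs relation to use of the device specifically |
| SAP section 15 listing | Yes; device and drug are shown separately |
| mSQAAQ outcome and planned sample size of 51 | No |

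**Side by side on follow-up.** Protocol 12.3 and 12.7 split follow-up by relatedness. The synopsis and 9.2.5 give 7 days for participants with AEs and make no such split. The 7 days are also counted differently: from the AE in the synopsis and 12.3, from the visit in 9.2.5 and 12.7.

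**The case against.** The strongest reply is that the plain reading gives a coherent rule. The two categories are then exact complements, and the rule is cautious: it labels too many events as related, which keeps non-serious AEs on the until-resolved track. A sensitive rule can be a deliberate choice in a one-visit device study. Protocol 12.1 also only fixes what counts as an AE and does not formally contradict a later relatedness rule. Much of this stands. The wording is usable, and its error runs in the cautious direction. But a label that nearly every post-pen event receives does not serve the stated aim of judging the likelihood of relatedness, and nothing in the protocol says that this breadth is intended.

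A second reply is that injections go into a pad, so without accidental exposure there may be no drug exposure to be temporally related to. That is fair for the drug. But 12.5 asks about the device or the drug, and a link in time to the device is enough.

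A reader might also infer stronger points that the documents do not support:

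- *The categories necessarily overlap.* They do so in one of the four readings, and not in the plain one.
- *The label drives follow-up of serious AEs or expedited reporting.* Serious AEs are followed until resolved whatever the label, and 12.9 does not refer to 12.5.
- *Device and drug relationships cannot be told apart.* SAP section 15 lists them separately, 12.5 does not forbid applying its criteria to each, and the AE case report form is not among the documents.
- *All of the approximately 56 enrolled participants are affected.* That is the number under the rule. Only a participant with a non-serious AE after pen handling could change follow-up track.

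**Conclusion.** The concern holds in a limited form. On its plain reading, Protocol 12.5 makes timing alone sufficient for *Related*. In a study with a single-visit collection window, the label then does not separate coincidental events from those caused by the device or the drug. Other readings of the same words produce an overlap, a gap or the opposite label, so the text also leaves room for inconsistent classification.

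The size is bounded. It concerns nearly every AE that starts after pen handling, but the documents give no AE rate, so no count can be stated. The consequences are limited to the follow-up track of non-serious AEs, classification as an ADE and the relationship columns of a descriptive listing. No comparison or decision rule in the SAP uses relatedness.

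The conclusion assumes the ordinary inclusive meaning of and/or, and that no definition outside these documents, such as case report form instructions, already requires a causal element.

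**What to change.** In Protocol 12.5, define *Related* as a reasonable possibility that the device or the drug caused the event, and *Not related* as the absence of such a possibility, so that each event falls in exactly one category. State that timing is supporting evidence and not sufficient by itself. State also that the judgement is made once for the device and once for the drug, and check that the AE case report form has both fields, to match SAP section 15. 'Reasonable possibility' is wording proposed here; the documents do not prescribe it.

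The cost is a few sentences in 12.5 and a check of the form, with no added visits, staff or participants. The downside is that fewer timing-only events will be labelled related, and those that are non-serious will move to the follow-up track for unrelated AEs. The sponsor should therefore reconcile the follow-up statements in the synopsis, 9.2.5, 12.3 and 12.7 in the same amendment.
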